Study design

randomized controlled double-blind parallel-group multi-centre study

Medication/device *If applicable*

Not applicable (enteral and parenteral nutrition, commercially available)

The subjects

Number of subjects

- Colorectal cancer (CRC) st. III - IV (TNM system) with cachexia
- Non-small cell lung cancer (NSCLC) st. III - IV (TNM system) with cachexia

120 subjects in each group, 60 controls and 60 Nutrition Therapy patients, based on statistical power. 20% extra patients were added to this number to account for dropouts.

Investigational group (Group A)

At the time of diagnosis, patients will immediately be screened and started with Nutrition Therapy if assigned to group A. This regimen will stay in place for 3 months, after which a switch will be made towards normal dietary counselling. Nutrition Therapy can be given orally, parenterally or via tube feeding, depending on the patient's status and aims at matching caloric Intake with Resting Energy Expenditure. Moreover, a switch between these modalities is possible during these 3 months. Afterwards, standard dietary counselling will be given during the remainder of the study. Follow-up will last 1 year. If one year after the last enrolment the study shows a large difference with the control group, the study will be stopped for ethical reasons.

Reference group (Group B)

At the time of diagnosis, patients will immediately be screened and started with standard dietary counselling for 2 years if assigned to group B. Dietary intervention can be orally, parenterally or via tube feeding, depending on the patient's status. Moreover, a switch between these modalities is possible during these 3 months. Follow-up will last 1 year. If one year after the last enrolment the study shows a large difference with the control group, the study will be stopped for ethical reasons.

Both Groups:

Oncological treatment will be performed at the discretion of the participating specialists, following the ESMO guidelines. Although an open label study, the oncologic treatment will not be related to the dietary regimens.

Inclusion is to take place in a period of one year. The duration of the study for each subject from randomisation to end of treatment is three months and a follow up period of nine months, for a total of one year per patient. Afterwards, analysis will take place.

Power calculation:

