96 patients per cancer group (48 controls and 48 nutrition therapy), supplemented with 20% per group to take dropouts into account.

Inclusion criteria

- > 18 years
- Male and female
- CRC or NSCLC before chemo- or radiotherapy is started (naive to treatment), but surgery may already have been performed
- CRC or NSCLC relapse > 3 months after initial oncologic therapy
- Oncologic cachexia (undesired weight loss > 5% in less than 6 months)
- Written informed consent / ability to give informed consent

Exclusion criteria

- concomitant second malignancy
- uncertainty of diagnosis of CRC or NSCLC
- patient unfit for chemotherapy
- patient unfit for radiotherapy
- patient unfit for surgery
- palliative treatment or terminal patient (life expectancy < 3 months)
- patient already participating in another study
- Pregnancy / lactation
- Any other pathology present that causes the patient to be unfit for oncologic therapy (e.g. end-stage renal failure, severe COLD, severe heart failure)
- Unable to adhere to protocol instructions (e.g. language barrier)
- Investigator's uncertainty about the willingness or ability of the patient to comply with the protocol requirements
- Participation in any other studies involving investigational or marketed products concomitantly or within two weeks prior to entry into the study

Replacement of subjects

In case of dropout, subjects will be censored on the Kaplan-Meier curves.

[figure not shown]
Restrictions and prohibitions for the subjects

None.

Procedures

See below, to be performed at the oncology consultation.

Flowchart

systematic overview of the study: planned tests per visit of the subjects

Expected total duration of the trial: 2 year (inclusion).

Supervising MD during the tests: Principal Investigator: [name] or co-investigator: [name].

Randomisation/blinding

Computerized randomization, validated for clinical trials, are used.

Prior and concomitant therapy

See "Inclusion and Exclusion criteria". All other concomitant therapy is allowed.

Study analysis

Sample size calculation

The statistical power was calculated based on the pilot trial.

Analysis of the samples

Outcome parameters:

• Body weight
• BIA Bio-Electrical Impedance Analysis
• Blood Pressure
• Blood Sample Analysis
• Caloric and Nitrogen intake
• Indirect Calorimetry
• Sensewear ®
• Body weight
• BIA Bio-Electrical Impedance Analysis
• Blood Pressure
• Blood Sample Analysis
• Indirect Calorimetry
• Body weight, mortality, morbidity.

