- Primary: weight stabilisation, morbidity and mortality
- Secondary: Quality of Life (QoL 36)

Statistical analysis

2-tailed, paired t-tests will be used for statistical analysis.

Quality control and quality assurance

The quality control is performed by the certified and experienced research unit of the Intensive Care Department.

Publication policy

All rights belong to the PI and thus to the VUB/the UZ Brussel.

Protocol Amendment dd 12/06/2017

Background:

Due to lack of patients with 5% weight loss in 6 months and, by consequence, very low inclusion rate, it was decided to amend the protocol. To achieve this, a special cooperation with the department of Radiotherapy was established. The service sees many patients who lose weight during radiotherapy, partly because of cancer-related cachexia, but mostly due to the mucositis caused by radiotherapy itself, losing > 10% of their initial body weight (at the start of their therapy). This is especially seen in cancers of head and neck, oesophagus and stomach. Radiotherapy is performed on working days and treatments typically last 5-7 weeks (depending on indication).

Amendment:

- Inclusion of patients with colorectal, lung and pancreatic cancer will be changed to: Inclusion of patients with lung, gastric, oesophageal, head and neck and pancreatic cancer
- 5% weight loss over the past 6 months will be changed to: patients with the aforementioned cancers where radiotherapy will be part of their treatment (or will be the entire treatment)
- Duration of intervention of 3 months will be changed to: duration of intervention for the entire period of radiotherapy
- After recalculation of statistical power, only 48 patients will be needed instead of 96. With correction for dropouts, this will become 60 patients instead of 120. This means 30 controls and 30 patients in the intervention group.
- The amendment will be added to the registration at *clinicaltrials.gov*.

The procedure and flowchart will remain unchanged. Analysis of the data will remain: in whole, per cancer and per sex (the latter two criteria requiring 60 patients in each group).

Protocol Amendment dd 19/09/2017

Background:

The study has seen much more inclusions and is running well thanks to the previous amendment. Due to a typo, the colorectal cancer group was unfortunately omitted. Also, the absolute difference of survival in the TiCaCo trial after one year was similar to that after the second year.

Amendment:

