- Colorectal cancer patients are still to be included. Otherwise, nothing changes concerning inclusion criteria.
- The follow-up will be shortened from 2 years to one year.
- The amendment will be added to the registration at *clinicaltrials.gov*.

Protocol Amendment dd 05/02/2019

Background:

The study needs 48 inclusions that remain in the study until the end. However, the number of dropouts is too high, severely compromising the study's statistical power. Therefore, an inclusion surplus of 20 - 25% is required.

Amendment:

- The inclusion period will be expanded to 31/12/2019 or the inclusion of 60 patients (including dropouts), whichever is sooner.
- The amendment will be added to the registration at *clinicaltrials.gov*.

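### The protocol keeps per-cancer and per-sex analyses that it says need 60 patients in each group, yet inclusion ends at 60 patients for the whole trial across six cancers

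*Protocol*

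**What the plan says.** The original plan sized each cancer group separately. Under Number of subjects it lists two, colorectal and non-small cell lung cancer, and gives "120 subjects in each group, 60 controls and 60 Nutrition Therapy patients, based on statistical power"; the figure includes a 20% allowance for patients who leave early. Under Power calculation it gives "96 patients per cancer group (48 controls and 48 nutrition therapy), supplemented with 20% per group to take dropouts into account".

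The amendment of 12/06/2017 widens entry to lung, gastric, oesophageal, head and neck, and pancreatic cancer. On size it says: "After recalculation of statistical power, only 48 patients will be needed instead of 96". Once the allowance for early leavers is added, enrolment falls from 120 to 60, divided equally at 30 per arm. The amendment does not say whether these figures are per cancer group or for the whole trial. On analysis it says: "Analysis of the data will remain: in whole, per cancer and per sex (the latter two criteria requiring 60 patients in each group".

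The amendment of 19/09/2017 restores colorectal cancer, which makes six sites. The amendment of 05/02/2019 says the study needs 48 patients who stay to the end, and closes inclusion on 31/12/2019 or at "the inclusion of 60 patients (including dropouts), whichever is sooner". No later text changes or withdraws the analyses by cancer and by sex.

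**The concern.** The protocol fixes the size that its subgroup analyses need and then sets an inclusion limit that makes this size unreachable, with no fallback. A reader cannot tell whether inference by cancer and by sex has been abandoned or is still planned. If the sentence stands, a difference seen in one small site or one sex could later be presented as a planned analysis, although the protocol's own requirement for that analysis was never met.

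A second difficulty lies in the sample-size statement itself. The figures being replaced (96 and 120) were per cancer group. The replacements (48 and 60) carry no unit in June 2017 and are trial totals by February 2019. The size of the reduction therefore cannot be read from the document.

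**Working it through.** **1. The plan's own dropout step.** Inputs: 96 and 48 evaluable patients, 20% dropout. Formula: N / (1 − d).
- Original: 96 / 0.80 = 120.
- Amended: 48 / 0.80 = 60, i.e. 30 per arm.

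Both stated figures are reproduced. The base figures 96 and 48 cannot be checked, because the protocol gives no effect size, SD, alpha or power; it names only the pilot trial as the source.

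**2. Required against available.** Inputs: 60 per group (amendment of 12/06/2017); six cancers (five in that amendment, plus colorectal from 19/09/2017); 60 patients at most, 48 completers (amendment of 05/02/2019).

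| Analysis | Needed | Available | Average per subgroup, enrolled | Average per subgroup, completers |
|---|---|---|---|---|
| Per cancer | 6 × 60 = 360 | 60 | 60 / 6 = 10 | 48 / 6 = 8 (4 per arm) |
| Per sex | 2 × 60 = 120 | 60 | 60 / 2 = 30 | 48 / 2 = 24 (12 per arm) |

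Both sexes cannot reach 60. One cancer could, but only if the other five enrolled nobody. If the word group in the bracket means a randomised arm, the need is still at least 2 × 60 = 120. The conflict therefore holds on each reading.

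**3. The unit of the reduction.** There are two ways to read the June 2017 figures.
- *Per cancer group.* 48 replaces 96 and 60 replaces 120 like for like, and the halving is correct. Six sites would then need 360 enrolled, and the 2019 limit of 60 contradicts it.
- *Whole trial.* The 2019 limit agrees, but the comparison sets a trial total against a per-cancer figure.

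The earlier total is itself uncertain. Number of subjects lists two cancers: 2 × 96 = 192 evaluable and 2 × 120 = 240 enrolled. The amendment of 12/06/2017 describes the population being replaced as three cancers (colorectal, lung and pancreatic): 3 × 96 = 288 and 3 × 120 = 360.

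**4. Illustration of what the subgroups could show.** The assumptions are ours, not the protocol's: two-sided 5% alpha, unpaired two-sample t-test, continuous outcome, 1:1 allocation, equal splits by site and sex, completers throughout, and 80% power overall at 24 per arm. Power comes from the noncentral t distribution with noncentrality δ × √(n/2) and 2n − 2 degrees of freedom, where n is the number per arm and δ the difference in SD units.
- 24 per arm: 80% power corresponds to δ = 0.83.
- One sex, 12 v 12: power at δ = 0.83 is 49%.
- One site, 4 v 4: power at δ = 0.83 is 17%; the difference detectable with 80% power is 2.4 SD.

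If the overall power is taken as 90% instead (δ = 0.96), the same formula gives about 61% per sex and 21% per site.

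**The case against.** The strongest reply is that the bracket states a condition, not a promise: analysis by cancer and by sex would need 60 per group and otherwise stays descriptive. The protocol nowhere calls these analyses confirmatory, descriptive summaries remain possible at any size, and the whole-population analysis is untouched. Rules for subgroup testing and multiplicity are commonly left to a statistical analysis plan, which is not at hand. All of this stands, and it limits the point. It does not remove it: the sentence says the analyses remain, the condition is unattainable for both sexes and for at least five of the six cancers, and nothing says what follows.

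Three stronger readings are tempting, and the document does not support them.
- *The sample size was cut four-fold and reported as a halving.* This needs June 2017's 48 and 60 to be trial-wide and the earlier plan to have had two cancers (192 to 48, 240 to 60). The first is not stated in that amendment, and the second conflicts with its own mention of three.
- *The protocol promises confirmatory answers by cancer and sex.* It speaks only of analysis and attaches no significance claim to the subgroups.
- *Nine tests at 5% carry a 37% false-positive risk.* The figure 1 − 0.95⁹ = 37% assumes nine independent tests (one overall, six sites, two sexes). These populations overlap, so it is not the error rate of this plan, and the document does not say that each is tested at 5%.

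**Conclusion.** The contradiction is established from the protocol's own numbers. The analyses by cancer and by sex cannot be delivered at the size the protocol says they require: 360 and 120 patients against at most 60. What fails is the stated size, not the possibility of describing subgroups. Separately, the unit of the amended sample size is ambiguous: either the halving compares unlike units, or the 2019 limit contradicts it. The document does not settle which.

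The 360 and 120 rest only on reading the bracket as 60 per cancer and 60 per sex; on a per-arm reading the shortfall remains. The limit of 60 comes from the 2019 amendment and the sixth cancer from September 2017, so the conflict is between amendments that are all in force. The power figures (about 49% per sex, 17% per site) depend on the assumptions listed with them. They do not cover morbidity or mortality, which are also named as primary outcomes, and they show scale only. Whether 48 is enough for the whole-population analysis can be neither confirmed nor refuted from this document.

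**What to change.** Replace the analysis sentence in the amendment of 12/06/2017 with:

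> The primary analysis is in the whole randomised population (60 randomised in total, 48 completers). The 60 per group needed for inference by cancer or by sex will not be reached; effects by tumour site and sex are descriptive only, as estimates with confidence intervals and no significance claim.

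In the same place, state that 48 and 60 are totals for the trial and that the earlier 96 and 120 were per cancer group. Before quoting an earlier total, reconcile whether the earlier plan had two cancers (192 evaluable, 240 enrolled) or three (288 and 360).

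The cost is wording only. Recruitment, randomisation and patient care do not change. The trial gives up subgroup claims that it could not have supported.
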